## 16.0 Quality Assurance Procedures and Participant Confidentiality

### 16.1 Overview of Quality Assurance Procedures

We have a number of features in place to ensure a high level of quality in our intervention study.

**Quality Assurance Procedures for Implementation of Intervention Sessions.** First, we are using a randomization procedure and a stringent control condition that equates for therapist time and attention. Second, we will assess patient and partner intervention credibility to determine whether credibility of both conditions is equivalent (see 16.2 for further explanation). Third, we are employing a manualized approach to treatment, in which all interventionists will use the manual to deliver both intervention conditions. Adherence to the manual will be assessed using the procedure described below in section 16.3. Fourth, the PI and site PI's will not be involved in any assessment procedures to ensure adequate blinding; similarly, the interventionists will advise participants explicitly not to share their responses to credibility items (Program Evaluation Form) or the Materials Review (e.g., homework completion) with the interventionists, which could bias participant reports. Interventionists must know which condition participants are receiving because they themselves deliver them (and in this way, cannot be truly blinded like with a placebo drug study). However, in the training of interventionists, we will emphasize that both conditions are likely to be perceived as helpful by participants and will refer to the conditions as "Group 1" and "Group 2" as opposed to "active condition" and "control condition", thus attempting to reduce interventionist bias in favor of the active condition. Fifth, the intervention sessions will be delivered by experienced interventionists with a Master's degree or PhD in a mental health profession who have experience in counseling, and preferably with experience in delivering manualized individual or couple-based interventions, thus ensuring a high level of experience and training in the interventionists delivering the interventions (see more detailed descriptions of the backgrounds of interventions in the Interventionists section (4.3.1). Experience in delivering manualized interventions is important because delivery of such interventions entails a fine balance between rapport-building and attending to the couples' needs and adherence to the intervention protocol. Finally, all interventionists will be trained to deliver both interventions (Intimacy Enhancement; Living Healthy Together). Interventionists will be trained by the PI and allowed to begin delivering sessions only once approved by the PI. Training will include role-plays of these sessions to ensure that the interventionists have had a chance for skills practice and feedback prior to leading sessions. Regular supervision sessions among the interventionists with the PI or [name] (or both) will be held once the interventionists have begun to lead sessions with couples and will ensure a forum for ongoing discussion of cases, solving problems or answering questions about delivery of the intervention, and to reinforce use of the intervention manuals. During supervision, the interventionists and supervisors will regularly discuss the extent to which the interventionists were able to adhere successfully to the manual through using session checklists.

**Quality Assurance Procedures for Other Study Aspects.** First, to promote transparency, the trial will be registered on clinicaltrials.gov and a protocol paper will be published. Second, we have designed standardized procedures for every aspect of study administration, from the candidate screening process to administration of the study conditions. Third, all outcome measures have demonstrated excellent psychometric properties and have prior research supporting their appropriateness in the study population and sensitivity to interventions. Fourth, REDCap, a secure web-based application, will be

used for data collection and for randomization, with an automated procedure that limits prediction of allocation and protects masking of allocations. Finally, to facilitate unbiased data collection and analysis the following steps are taken: 1) the data analyst will conduct outcome data analyses on data in which study condition is masked; 2) outcome data collection is completed in an automated fashion using REDCap, minimizing the need for contact with participants to collect study data; 3) if needed, manual data collection will be completed by study staff for whom the participant's assignment is masked to the extent possible. On an annual basis, adverse events will be reviewed across study conditions. During the annual review of adverse events, the presence of significant between-group differences could potentially warrant unmasking of the study conditions by the study biostatistician. As with most behavioral interventions, study interventionists, intervention supervisors (site PI's), and participants are not blind to study condition.

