#### 4.3 Overview of Randomization and Intervention Conditions

Couples will be randomized with an allocation ratio of 1:1 to either the IE or the Educational Control (Living Healthy Together) condition with stratification by age at diagnosis ( $\leq 45$  vs.  $> 45$ ) using the age obtained from the medical record (or by the patient during screening, if age at diagnosis is not available in the medical record). The statistician ([name]) will generate the randomization sequences using an automated randomization procedure in REDCap that limits prediction of allocation and protects masking of allocations. Randomization in blocks of four will guarantee that after every four assignments the study arms will have equal numbers. Separate randomization tables will be used for FCCC, Duke, and community participants to minimize the potential for unequal randomization by site.

Randomization will occur once both members of the couple have consented, completed baseline surveys, and are scheduled for their first intervention session. Randomization will occur centrally at the primary site by a staff member uninvolved in recruitment (to reduce the potential for bias in randomizing participants onto certain conditions). Once randomized, the couple will be sent sealed study materials along with the instructions to leave the envelopes sealed until they “meet” with their interventionist for session 1. It is important to keep the study condition a secret from participants until Session 1 to reduce the chances for unequal drop-out prior to Session 1, which could occur if patients/partners are more motivated to attend sessions in one study group as opposed to the other.

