##### 4.3.1 Interventionists

All sessions will be conducted with the couple by trained interventionists with a Masters or doctoral degree in psychology or clinical social work and certified competent in the interventions by the PI. As established in our pilot trial, interventionist training consists of (a) background readings on key topics including breast cancer stages and treatments, common sexual and non-sexual side effects (e.g., stress, fatigue), sexual response, key techniques such as cognitive behavioral couple therapy and sensate focus therapy, theoretical models, and cultural issues in couple and sex therapy; (b) an in-person workshop or web conference which includes review of readings, protocols, and specific skills (e.g., communication skills training), role plays, and discussions, (c) listening to a tape of a well-executed case for each condition, and (d) complete IE and LHT test cases using intervention materials. During the trial, [name] and/or [name] will hold regular supervision sessions among the interventionists to ensure adequate quality of the delivered interventions. Interventionists will take standardized clinical notes on their sessions not containing identifying participant information and these notes will be discussed during supervision sessions. All supervision sessions are confidential; no identifiable information about participants is retained in clinical notes or supervision records. The quality assurance procedures regarding the delivery of the intervention are described further in section 16.0.

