### **13.2 Statistical Analyses for Aim 1 (Primary Aim; Effects of IE Intervention on Patient Sexual Function)**

The primary analysis will examine whether, relative to the LHT condition, the IE condition leads to greater increases in the primary outcome of patient sexual function at all three post-treatment assessments (T2-4; post-treatment; 3-month FU; 6-month FU). We will also examine specific domains of sexual function (satisfaction, desire, arousal, lubrication, orgasm, pain) separately. In a mixed effects regression model, study condition will serve as the independent variable and patient sexual function at each time point will serve as the dependent variable; pre-treatment sexual function will be included in the model as a covariate with time included as a categorical covariate. Intervention by time interaction effects will be included to test the intervention effect at each follow-up time. Subject-specific random intercepts will account for within-subject variability. Intervention effects on patient sexual function at each follow-up are tested using F tests of combined main and interaction effects.

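### Interventionists who know the arm deliver both conditions, but the plan does not say whether a couple's interventionist is fixed before randomisation, and no outcome model contains an interventionist term

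*Combined protocol and SAP*

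**What the plan says.** Delivery is meant to be crossed with arm. Section 16.1 states that "all interventionists will be trained to deliver both interventions" and that "all interventionists will use the manual to deliver both intervention conditions". The same section accepts that interventionists cannot be blinded, since they deliver the condition themselves. Section 4.3.1 describes their qualifications ("All sessions will be conducted with the couple by trained interventionists with a Masters or doctoral degree in psychology or clinical social work") but not how many there are.

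On timing, section 4.3 states: "Randomization will occur once both members of the couple have consented, completed baseline surveys, and are scheduled for their first intervention session". It does not say whether a named interventionist is settled at that scheduling. The randomisation is stratified by age at diagnosis, and "Separate randomization tables will be used for FCCC, Duke, and community participants". Interventionist is not a stratification factor, and no section gives an assignment rule or a caseload target by arm.

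On analysis, section 13.2 says: "In a mixed effects regression model, study condition will serve as the independent variable". The other terms are baseline sexual function, time and the intervention-by-time interaction, and "Subject-specific random intercepts will account for within-subject variability". Section 13.3 follows the same approach for partner sexual function. Section 13.4 adds random intercepts for patient and partner and a residual correlation within the couple. None of these models contains interventionist. The power calculation in 13.8 makes no allowance for it.

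**The concern.** In a therapist-delivered trial the person delivering the sessions is a known source of variation in outcome. Crossing interventionists with arms protects the comparison from differences in general skill only if each interventionist's couples are spread similarly over the two arms. The protocol intends crossing but does not secure that balance. If the interventionist is chosen once the arm is known, for whatever practical reason, some may see mostly IE couples and others mostly LHT couples. The arm contrast then contains part of the difference between people, and a model without an interventionist term cannot separate the two.

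A second mechanism is distinct. Interventionists may differ in how large an IE-LHT difference they produce. Couples seen by the same person then share that deviation, and the planned standard error does not reflect it.

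**Working it through.** **Inputs from the documents.** Difference of 5 points, SD of change 8.2, 92 analysable couples at 6 months and two-sided alpha 0.05 (13.8); allocation 1:1 (4.3), so 46 per arm.

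**Assumptions, not in the documents.** The number of interventionists (K) and the share of outcome variance attached to them. The calculations compare 6-month change scores between two groups, as 13.8 does, and so approximate the 13.2 model.

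**1. The plan's own figure.** 120 × 0.76 = 91.2, which the plan takes as 92. SE = 8.2 × √(2/46) = 1.710. Normal power = Φ(5/1.710 − 1.96) = 83.3%; with the noncentral t on 90 df it is 82.5%. The stated 82% reproduces, with couples treated as independent.

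**2. Common skill effect, balanced crossing.** With variance share ρ, skill cancels from the contrast and the true variance is 2 × 8.2² × (1 − ρ)/46. For ρ = 0.01 to 0.10 the variance factor is 0.99 to 0.90, and the unadjusted test has type I error of 4.9% down to 3.9%. If interventionists are allocated independently of arm but not exactly balanced, simulation at ρ = 0.05 gives 5.2% (K = 4) and 4.7% (K = 6). Omitting interventionist does no harm here.

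**3. Common skill effect, skewed caseloads.** Suppose half the interventionists together see 75% of IE couples and 25% of LHT couples, and the other half the reverse.
- K = 4: each interventionist's share of the two arms differs by 37.5% − 12.5% = 25 percentage points. The variance added to the contrast is 4 × 0.25² × 0.05 × 8.2² = 0.84, an SD of 0.92 FSFI points.
- K = 6: the gap is 25% − 8.3% = 16.7 points. The added variance is 6 × 0.167² × 0.05 × 8.2² = 0.56, an SD of 0.75 points.
- Simulated type I error of the unadjusted test (20,000 runs) is 8.4% for K = 4 and 6.7% for K = 6.
- Adding interventionist as a factor returns it to about 5%.

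**4. Price of the factor.** With the factor, the variance of the contrast is 0.95 × 8.2² divided by 92 × p(1 − p), where p is each interventionist's IE proportion.
- Balanced (p = 0.5): SE = √(63.88/23) = 1.667, power Φ(5/1.667 − 1.96) = 85%.
- Skewed (p = 0.75 or 0.25): SE = √(63.88/17.25) = 1.924, power Φ(5/1.924 − 1.96) = 74%.

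The factor corrects the error rate under skew but costs power, so preventing the skew is the better protection.

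**5. Arm-by-interventionist effect.** Let the IE-LHT difference vary between interventionists with variance w × 8.2². For w = 0.025 to 0.05 its SD is 1.3 to 1.8 points. Then Var = 2 × 8.2²/46 + w × 8.2²/K, and type I error = 2 × (1 − Φ(1.987 × 1.710/SE)).

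| K | w | SE | Type I error |
|---|---|---|---|
| 8 | 0.025 | 1.770 | 5.5% |
| 4 | 0.05 | 1.940 | 8.0% |
| 3 | 0.05 | 2.011 | 9.1% |

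The main-effect factor does not help here. In simulation with K = 4 and w = 0.05 under balanced crossing, type I error is 8.4% without it and 8.2% with it. The size also depends on how the share is defined. Placing an independent 5% in each arm, rather than 5% on the contrast, gives 11.2% for K = 4.

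**The case against.** The strongest reply is that the design already limits the problem. Interventionists are certified and complete test cases in both conditions (4.3.1). They follow manuals, are supervised regularly and hear the arms described in neutral terms (16.1). An independent reviewer checks 10-20% of cases against an 85% adherence threshold (16.3). Session 1 is scheduled before randomisation, so the interventionist may in practice already be fixed. All of this stands, and it makes skill-based assignment and a large arm-by-interventionist effect less likely. None of it is an assignment rule or a model term, however, and the protocol does not say that scheduling names the interventionist.

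A reader might infer three stronger things that the documents do not support:
- **Omitting interventionist in itself makes the primary standard error too small.** Step 2 shows that under balanced crossing the unadjusted test is, if anything, conservative.
- **The trial relies on a few interventionists, with nothing linking a couple to one before the arm is known.** No number is given, and on the link the text is silent rather than negative.
- **The 82% power is wrong.** Under the step 5 assumptions the planned test, Φ((5 − 1.987 × 1.710)/SE), would still reject at a true 5-point difference 78.7% to 81.7% of the time, against 82.6% on the same approximation with no such effect. The lower figures, Φ(5/SE − 1.96) = 70% to 81%, belong to a recalibrated test with known variance, which is not the planned one.

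It is also fair to object that naming the interventionist early and adding a factor do not cure the step 5 heterogeneity. That is correct, and it is why the sensitivity analysis is a separate item.

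**Conclusion.** The point holds in a limited form. The protocol leaves open whether interventionists, who know the arm, are assigned before or after randomisation, and the outcome models could not correct a skew in caseload. Under an assumed 75/25 split, 5% of variance and 4 to 6 interventionists, type I error is about 7% to 9%; with balanced caseloads and a common skill effect there is no harm. Separately, an assumed 3 to 8 interventionists and an arm-by-interventionist variance of 2.5-5% would put it at about 5.5% to 9%. The documents show neither a skew nor such heterogeneity, so these figures measure exposure rather than an established error. The change is worth making because the protection is cheap and the timing in 4.3 already allows it.

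**What to change.** 1. In 4.3, state that a named interventionist is assigned and recorded when session 1 is scheduled, before randomisation. Keep that assignment for analysis even if someone else has to step in.
2. In 13.2 to 13.4, add interventionist as a factor.
3. Report the number of couples per interventionist by arm.
4. Prespecify one sensitivity analysis of the primary outcome with a random arm-by-interventionist effect, and state in advance that its variance will be imprecise if interventionists are few.

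**Cost.** One recorded field and a few sentences in the plan; K − 1 degrees of freedom (2 to 7 for 3 to 8 interventionists); slightly less freedom in scheduling; and some loss of power from the factor if caseloads are skewed all the same (step 4).

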### **16.2 Intervention Credibility**

Intervention credibility refers to the extent to which the intervention conditions are both perceived as by participants as credible and likely to be helpful. Participants will complete a 3-item Program Evaluation Form adapted from those used in other randomized controlled trials conducted by the PI and her colleagues to assess credibility immediately following session 1 and again at the post-intervention survey through REDCap, separately by patients and partners using online links. Data from this form will be analyzed after overall study data collection is completed to compare the credibility across the groups.

### **16.3 Intervention Adherence**

Adherence refers to the extent to which the interventionist delivers the intervention according to the intervention manuals. This differs from unstructured psychotherapy, and allows us to have faith that the interventions we intend to deliver are, in fact, delivered by interventionists as well as being replicable in future studies. Telephone sessions will be audio-recorded. A reviewer with familiarity with the material who is not involved in the delivery of the intervention ([name], Temple) will listen to a random sample of 10-20% of cases and evaluate the adherence of the interventionist to the manual using the session checklists as a guide. Adherence to session checklists  $\geq 85\%$  will be considered satisfactory. In addition to the independent reviewer sessions may also be listened to by members of the study team or consultants for educational or training purposes.

### **16.4 Participant Confidentiality**

Information about study subjects will be kept confidential and managed according to the requirements of the Health Insurance Portability and Accountability Act of 1996 (HIPAA). Those regulations required a signed subject authorization informing the subject of the following: The protected health information (PHI) that will be collected from patient; who will have access to that information and why; who will use or disclose that information; the rights of a research subject to revoke their authorization or use their PHI. In the event that a participant revokes authorization to collect or use PHI, the investigator, by regulation, retains the ability to use all information prior to the revocation of subject authorization. To ensure confidentiality identifiers will be recorded and used with electronic data collected and all records will be secured in a locked location.

## **17.0 Participant Informed Consent**

See separate Informed consent document

## **19.0. Appendices**

- Consent Forms
  - Web-based version of Consent
  - Paper version of Consent
- Surveys or Data Collection Tools
  - Self-Report Materials
